6.2 Efficacy Analysis Methods

Time-to-event variables (PFS, OS and DR) and their set time estimates (i.e., PFS 6/12 and OS 12/24) will be analyzed according to the Kaplan-Meier method.

The stratified log-rank test, using actual values for all randomization strata variables, on the ITT population will be primarily used to compare the time-to-event variables. If the actual value is not a pre-defined category the value will be added to the most similar category (e.g., patients with more than three prior chemotherapy lines will be included in the 3-lines category).

Unstratified log-rank tests will also be calculated as supportive analyses.

The symmetry of tumor evaluations between the different arms will be examined. Wilcoxon test to compare time to disease assessments between treatment arms will be used to assess symmetry of evaluations. Moreover, Kaplan-Meier curves of the time from randomization and first and second disease assessment will be plotted. If necessary, internal symmetry between the two different treatments in the control arm will be checked following the same approach.

Cox regression will be used to calculate the risk reduction (PFS, OS and DR) and to evaluate the influence of the stratification variables and other potential prognostic factors on the time-to-event efficacy endpoints.

Counts and percentages, with their corresponding exact 95% confidence intervals, will be calculated for the binomial endpoints (i.e., response rate). The Fisher's exact test (univariate analyses) and logistic regressions will be used to compare the response rates.

Waterfall plots will be used to describe the best variation of the sum of target lesions diameters during the treatment.

Multivariate models (main effects or including interaction terms, if appropriate) will include all stratification factors and/or prognostic factors/covariates widely reported and recognized by the scientific community: treatment (PM01183 vs. control), ECOG PS (0 vs. ≥ 1 or coded as 0 vs. 1 vs. 2) prior platinum-free interval (1-3 months vs. >3 months or used as continuous variable), prior chemotherapy (1-2 vs. 3 lines or coded as 1 vs. 2 vs. 3), geographical area (USA vs. Europe vs. rest of the world), investigator's preference for the control arm (Topotecan vs. PLD), age, age at diagnosis, race (caucasian vs. other), histology type (serous/papillary vs. other), histology grade (poorly/undifferentiated vs. other), primary tumor site (ovarian vs. other), FIGO stage at diagnosis (metastatic/locally advanced [stage III] vs. other), FIGO stage at study entry (metastatic vs. locally advanced [stage III]/other), BRCA status (mutated vs. other), clinical/radiological signs of intestinal subocclusion at entry (yes vs. no), site of current disease: lung/liver (yes vs. no), liver metastases (yes vs. no), number of prior metastatic sites (≤ 2 vs. >2), body mass index (BMI), height, weight, body surface area (BSA), time from diagnosis to first infusion, prior cytoreduction (optimal vs. suboptimal vs. no surgery), prior radiotherapy (yes vs. no), platinum resistance (primary vs. secondary), clinically evidence of ascites at baseline (yes vs. no), time elapsed from last dose of last prior platinum-containing regimen to randomization, prior antiangiogenic treatment

with bevacizumab (yes vs. no), prior PARPi (yes vs. no), presence of any bulky (< 50 mm vs. \geq 50 mm) lesion at baseline, measurable disease (yes vs. no), sum of all target lesion diameters, baseline CA-125, albumin value at baseline, PFS prior line, response to last platinum therapy (yes vs. no) and baseline global QoL. In addition, continuous variables categorized as discrete variables will also be investigated in the continuum range and if the adjustment is better then the continuous variable will be selected in the model.

All variables with a good percentage of valid cases (approximately \geq 90%) will be included in the multivariate analysis. Within the multivariate stepwise Logistic/Cox regression analysis, the chosen significance level for entering an explanatory variable into the model will be 0.05 (for all variables not in the model, the one with the smallest p-value will be entered if the p-value is less than or equal to the specified significance level). The significance level for removing an explanatory variable from the model will be 0.05 (for all variables in the model, the one with the largest p-value will be removed if the p-value exceeds the specified significance level). The parameter estimates, hazard ratios/odds ratios and p-values of the variables retained in the model will be presented.

Forest plots for PFS and OS summarizing main results, stratification and factors/covariates used in multivariate analyses will be plotted⁽²⁾.

Median follow-up (FU) time for PFS and OS will be calculated in the descriptive way, only taking into account the censored values and using the Kaplan-Meier method for reversing the censoring values as described by Parmar⁽³⁾.

Concordance between IRC and IA PFS assessments will be evaluated by means of Kaplan-Meier curves. Forest plots for response will also be performed adapting them to show relevant information (e.g. percentages will be shown instead of medians).

Sensitivity analyses for different PFS censoring will be performed. The following approaches will be calculated: 1) Date of progression based on scheduled time instead of recorded date (e.g. if progression occurs in the eleventh week and assessment would have to be done in the eighth week then the expected date is used instead of the actual date); 2) First date of progression combining IRC and IA assessments (e.g. the lowest date between IRC and IA is used); and 3) Date of progression moved to the prior tumor assessment date (e.g. if progression has not been documented in the second assessment and is documented in the third assessment then progression date is moved to the second assessment).

Proportional hazard assumption for PFS and OS will be checked by means of a Cox regression including treatment and its interaction with survival time⁽⁴⁾. In case of strong rejection of proportionality, then restricted mean survival estimates will also be calculated in addition to HR^(5,6).

Main summary of efficacy analyses

Endpoint	Population	Statistics
PFS by IRC (primary endpoint)	ITT population	-Stratified log rank test
OS	ITT population	-Stratified log rank test -Unstratified log rank test -Kaplan Meier estimates -Univariate Cox regression -Multivariate Cox regression
PFS by IRC/IA	ITT population	-Stratified log rank test (IA) -Unstratified log rank test -Kaplan Meier estimates -Univariate Cox regression -Multivariate Cox regression

Endpoint	Population	Statistics
Response rate by IRC/IA	ITT population	-Fisher exact test -Logistic regression
Duration of response by IRC/IA	ITT population (in patients achieving a response)	-Unstratified log rank test -Kaplan Meier estimates

ITT: Intention-to-treat; IRC: Independent Review Committee; IA: Investigator Assessment; PFS: Progression Free Survival; OS: Overall Survival

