5.2 Sample Size

This phase III clinical trial is designed to determine a statistically significant difference in PFS by IRC between PM01183 and a control arm with PLD or topotecan in ovarian cancer patients with platinum-resistant disease.

Patients will be randomized to receive PM01183 given as 3.2 mg/m² (Arm A) or either topotecan or PLD (Arm B).

The prospective assumptions are a 30% reduction in the relative risk of progression or death (HR=0.7) to be achieved with the experimental arm (PM01183), at a one-sided 2.5% significance level with at least 90% power, following exponential distributions and fulfilling the proportional hazard assumption. Median PFS with control arm is expected to be around 3.5 months. It is forecasted that an observed HR of approximately 0.8 will have enough power to reject the null hypothesis (HR=1).

Approximately 420 patients with platinum resistant ovarian cancer will be necessary to stratify and randomize at a 1:1 ratio over 18 months (~23 patients/month). The required 332 PFS events are expected to occur around six months after randomization of the last patient. Therefore, the IDMC meeting after the IRC review to test PFS is expected to occur about one year after randomization of the last patient.

With the prospective assumptions above mentioned, about 175 PFS events are expected in the control arm and 157 in the PM01183 treatment arm.

The IDMC will review the results of the analyses. The IRC will determine the patient's best response and assign the date of objective response or progression/censoring according to the RECIST v.1.1.

5.2.1 *Futility Analysis*

A futility analysis will be performed when 210 patients are recruited (i.e., ~105 patients enrolled in each arm). The recruitment will not be put on hold.

In the futility analysis, the sponsor will make no claim of efficacy, consequently this futility analysis and the final analysis to reject the null hypothesis ($HR=1$) are planned; the significance level will be determined by the actual number of observed events by IR. To maintain scientific integrity, type II error will be controlled by a spending function defined by O'Brien-Fleming boundaries. Following the prospective assumptions, the interim analysis will occur at less than one year after start of recruitment. At this moment, with the available information collected after balancing efficacy and safety, the IDMC might recommend stopping the trial.

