Overall survival (OS) is defined as the time from the date of randomization to the date of death (death event) or last contact (in this case, survival will be censored on that date). If applicable and more than one OS analysis is performed type I error will be controlled by spending function defined by O'Brien-Fleming boundaries. Counting out subsequent therapies impact, sample size is powered to detect OS differences in the 20-30% range. Final OS analysis is planned 24 months after randomization of last patient (planned end of study date).

Landmark analyses of PFS at 6/12 months by IRC/IA and OS at 12/24 months will be the Kaplan-Meier estimates of the probability of being free from progression and/or alive at these time points.

Best antitumor response by IRC/IA will be the best response obtained in any evaluation according to RECIST v.1.1.

Radiological antitumor activity will be assessed using the RECIST v. 1.1 on a set of measurable lesions identified at baseline as target lesions, and/or non-measurable lesions (if any) identified at baseline as non-target lesions and followed until disease progression (PD) by the appropriate method [computed tomography (CT) scan or magnetic resonance imaging (MRI)].

Duration of response (DR) will be calculated from the date of first documentation of response (complete or partial response, whichever comes first) to the date of documented PD or death. The censoring rules defined above for PFS will be used for duration of response.

Assessments must be done consistently in both treatment arms to ensure a symmetrical assessment of tumor response and progression. Every effort should be made to ensure

that these assessments are done on the required date. Time to n^{th} (i.e. 1, 2, 3...) disease assessment is defined as weeks between randomization and the recorded date of the n^{th} radiology assessment after randomization.

Best response according to tumor marker evaluation (CA-125) will be the best response obtained according to GCIG criteria⁽¹⁾. Irrespectively of treatment arm, tumor marker assessment will be performed symmetrically at baseline and every eight weeks from randomization until evidence of PD.

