PR					
SD					
PD					
Unknown*					
CR+PR; n (%) and binomial exact 95% confidence interval					

(*) Including NE, non-responders and insufficient data available.

Table 11.3.1.30 Multivariate analysis of response rate by IRC (Stratification factors and treatment arm)

Table 11.3.1.31 Multivariate analysis of response rate by IRC

(See list of covariates in section 6.2).

A forest plot (Figure 11.3.1.32) summarizing main results, stratification factors and covariates in terms of response by IRC will be plotted.

A waterfall plot (Figure 11.3.1.33) describing the best variation of the sum of target lesions during the treatment will be plotted.

Table 11.3.1.34 DR by IRC

	PM01183	Control	Parameter	p-value
N				
Events				
Censored				
Median DR (95% CI)			Log-Rank: HR (95% CI) :	LR: HR:

Objective response and duration of response by IA

Table 11.3.1.35 Response rate by IA

Response	PM01183		Control		p-value
	N	%	N	%	
CR					
PR					
SD					
PD					
Unknown*					
CR+PR; n (%) and binomial exact 95% confidence interval					

(*) Including NE, non-responders and insufficient data available.

Table 11.3.1.36 Multivariate analysis of response rate by IA (Stratification factors and treatment arm)

Table 11.3.1.37 Multivariate analysis of response rate by IA

Analysis of maximum likelihood estimates								
Variable label	Variable values	DF	Estimate	Standard error	Wald chi-square	Pr > ChiSq	Odds ratio estimate	95% Wald confidence limits

(See list of covariates in section 6.2).

A forest plot (Figure 11.3.1.38) summarizing main results, stratification factors and covariates in terms of response by IA will be plotted.

A waterfall plot (Figure 11.3.1.39) describing the best variation of the sum of target lesions during the treatment will be plotted.

Table 11.3.1.40 DR by IA

	PM01183	Control	Parameter	p-value
N				
Events				
Censored				
Median DR (95% CI)			Log-Rank: HR (95% CI) :	LR: HR:

CA-125 Objective response

Table 11.3.1.41 CA-125 response rate

Response	PM01183		Control		p-value
	N	%	N	%	
CR					
PR					
SD					
PD					
Unknown*					
CR+PR; n (%) and binomial exact 95% confidence interval					

(*) Including NE, non-responders and insufficient data available.

Table 11.3.1.42 CA-125 response rate (excluding UK category)

Response	PM01183		Control		p-value
	N	%	N	%	
CR					
PR					
SD					
PD					
CR+PR; n (%) and binomial exact 95% confidence interval					

Progression and censoring reasons by IRC/IA

Table 11.3.1.43 Progression type by IRC/IA

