Reason	IRC				IA			
	PM01183		Control		PM01183		Control	
	N	%	N	%	N	%	N	%
Target lesion								
Non-target lesion								
Death due to malignant disease								
Other*								

(*)Please specify.

Table 11.3.1.44 Censoring reason by IRC/IA

Reason	IRC				IA			
	PM01183		Control		PM01183		Control	
	N	%	N	%	N	%	N	%
Free of progression last tumor assessment								
Subsequent therapy before documented progression								
Not treated								
Other*								

(*)Please specify.

Subgroup analyses

Forest plots summarizing main results, stratification factors and covariates for the comparison between PM01183 and PLD will be plotted.

- Figure 11.3.1.45 PFS by IRC (PM01183 vs PLD)
- Figure 11.3.1.46 PFS by IA (PM01183 vs PLD)
- Figure 11.3.1.47 OS (PM01183 vs PLD)
- Figure 11.3.1.48 RR by IRC (PM01183 vs PLD)
- Figure 11.3.1.49 RR by IA (PM01183 vs PLD)
- Figure 11.3.1.50 DR by IRC (PM01183 vs PLD)
- Figure 11.3.1.51 DR by IA (PM01183 vs PLD)
- Figure 11.3.1.52 CA125 by IRC (PM01183 vs PLD)

Forest plots summarizing main results, stratification factors and covariates for the comparison between PM01183 and Topotecan will be plotted.

- Figure 11.3.1.53 PFS by IRC (PM01183 vs Topotecan)
- Figure 11.3.1.54 PFS by IA (PM01183 vs Topotecan)
- Figure 11.3.1.55 OS (PM01183 vs Topotecan)
- Figure 11.3.1.56 RR by IRC (PM01183 vs Topotecan)
- Figure 11.3.1.57 RR by IA (PM01183 vs Topotecan)
- Figure 11.3.1.58 DR by IRC (PM01183 vs Topotecan)
- Figure 11.3.1.59 DR by IA (PM01183 vs Topotecan)
- Figure 11.3.1.60 CA125 by IRC (PM01183 vs Topotecan)

Forest plots summarizing main results, stratification factors and covariates for the comparison between PM01183 and Control arm selecting patients who received as first subsequent therapy a platinum line will be plotted.

- Figure 11.3.1.61 PFS by IRC (PM01183 vs Control)
- Figure 11.3.1.62 PFS by IA (PM01183 vs Control)
- Figure 11.3.1.63 OS (PM01183 vs Control)

- Figure 11.3.1.64 RR by IRC (PM01183 vs Control)
- Figure 11.3.1.65 RR by IA (PM01183 vs Control)
- Figure 11.3.1.66 DR by IRC (PM01183 vs Control)
- Figure 11.3.1.67 DR by IA (PM01183 vs Control)
- Figure 11.3.1.68 CA125 by IRC (PM01183 vs Control)

In the forest plots continuous variables not categorized in the definition will be coded into two categories taking as reference the median value, below or equal the median value and above the median value.

Characteristics of responders

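### Duration of response is compared between arms by log-rank test and hazard ratio although it exists only in responders, so the hazard ratio mixes drug effect with responder selection

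*SAP*

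**What the plan says.** SAP 6.2 opens its methods with "Time-to-event variables (PFS, OS and DR) and their set time estimates", so DR is one of the time-to-event variables. The next paragraph says that the stratified log-rank test "on the ITT population will be primarily used to compare the time-to-event variables". Unstratified tests are supportive. It then adds that "Cox regression will be used to calculate the risk reduction (PFS, OS and DR"). Protocol 8.2.1 and the statistical methods part of the protocol synopsis carry the same plan.

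The endpoint itself starts at response. SAP 6.1 says: "Duration of response (DR) will be calculated from the date of first documentation of response". The summary table at the end of SAP 6.2 accordingly sets the DR population as "ITT population (in patients achieving a response"), and lists only an unstratified log-rank test and Kaplan-Meier estimates for it.

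The output shells in SAP 11.3 go further than that table. "Table 11.3.1.34 DR by IRC" and its investigator-assessed counterpart, Table 11.3.1.40, have a log-rank p-value and an HR with 95% CI and its own p-value. DR forest plots are planned against PLD (for example "Figure 11.3.1.50 DR by IRC (PM01183 vs PLD")), against topotecan, and in patients whose first subsequent therapy was platinum: Figures 11.3.1.50, .51, .58, .59, .66 and .67. SAP 8.9 classes these subgroup comparisons as exploratory. Nothing gives Tables 11.3.1.34 and 11.3.1.40 a descriptive label or mentions selection on response.

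**The concern.** Randomisation makes the arms comparable; it does not make the responders in the two arms comparable. If PM01183 produces more responses, its responder group will include patients who would not have responded on PLD or topotecan. If those patients respond for a shorter time, they pull down the PM01183 DR curve even when the drug lengthens response in every patient. An HR between the two responder groups is then partly a drug effect and partly a difference in who was admitted to the comparison. The term risk reduction suggests a causal reading that this contrast cannot bear.

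What is at stake is a pre-specified HR and p-value, likely to be reported beside the efficacy results, that could understate the effect on duration or point the wrong way.

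There is also a plain inconsistency. The SAP 6.2 text gives DR a stratified log-rank test and Cox regression; the SAP 6.2 table gives it an unstratified log-rank test and no Cox; the shells print an HR. The proportional hazards check in SAP 6.2 covers PFS and OS only, so the DR HR would go unchecked.

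**Working it through.** **1. The plan's own figure.** The documents give no sample size, power or alpha for DR. Their design figures concern PFS: HR 0.70 "at a one-sided 2.5% significance level with at least 90% power", 332 events. Schoenfeld's formula gives 4(1.960 + 1.282)² / (ln 0.70)² = 4 × 10.507 / 0.12722 = 330.4, so 331 against 332. The critical HR is exp(−2 × 1.96 / √332) = 0.806, which matches the stated value of about 0.8. The PFS design reproduces; none of it carries over to DR.

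**2. How much data DR would have.** There are about 210 patients per arm (SAP 5.2). Protocol 1.1 gives 10–15% response for single agents, so 21 to 32 control responders. Assume 15–30% on PM01183 (30% is the phase II platinum-resistant figure in protocol 1.3.1), so 32 to 63 responders. If every response is followed to its end, power for a DR HR of 0.70 at two-sided 5% is Φ(√(D·q(1−q)) × |ln 0.70| − 1.96), where D is total responders and q the control share:
- 10% versus 15%: D = 52.5, q = 0.40, power 24%.
- 15% versus 30%: D = 94.5, q = 1/3, power 37%.

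With about 25 and 50 responders, the 95% CI for the HR spans a factor of exp(1.96 × √(1/25 + 1/50)) = 1.6 either way.

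**3. Selection model A (all inputs assumed).** Each patient has a standard normal sensitivity S and responds if S exceeds an arm-specific threshold. Log duration is b·S plus noise with SD 0.5, and every duration is 10% longer on PM01183. Mean sensitivity among responders is φ(z)/p:
- 12% response: z = 1.175, mean 1.667.
- 24% response: z = 0.706, mean 1.295.

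The difference is 0.372, so the responder-only duration ratio (PM01183/control) is about 1.10 × exp(−0.372b). Simulated median ratios agree with this formula to within 0.005:

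| Response, control vs PM01183 | b = 0.3 | b = 0.5 | b = 0.8 |
|---|---|---|---|
| 12% vs 24% | 0.98 | 0.91 | 0.81 |
| 12% vs 18% | 1.03 | 0.99 | 0.93 |
| 12% vs 15% | 1.06 | 1.04 | 1.00 |

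The true ratio is 1.10 in every cell, so every cell is biased downwards, but not every cell reverses. At 12% versus 24%, reversal needs a true lengthening below about 12%, 20% and 35% for the three slopes. With b = 0 there is no bias. In the first row, mean time in response per randomised patient rises 1.97-, 1.84- and 1.67-fold, correctly favouring PM01183.

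**4. Selection model B (all inputs assumed).** The 12% who respond on either drug have median DR 6 months on control and a true HR of 0.80 on PM01183. The extra PM01183 responders have median DR 2, 3 or 4 months. All responses are followed to their end.

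| PM01183 response | Responder-only HR (2, 3, 4 months) | Mean time in response, all randomised |
|---|---|---|
| 21% | 1.17, 1.08, 1.00 | 1.6–1.8 months vs about 1.0 |
| 30% | 1.40, 1.24, 1.12 | 1.8–2.3 months vs about 1.0 |

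In simulated trials with 210 patients per arm, the DR comparison pointed against PM01183 in 50–75% of trials at 21% response and 67–94% at 30%. It was nominally significant in the wrong direction in 2–10% and 6–26%.

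**The case against.** The strongest reply is that nothing is decided on DR. It is secondary, with no alpha, power or claim attached. The primary test is PFS by IRC in all randomised patients, and OS and response rate also use the full ITT population, so a reader would see any imbalance in responders beside the DR table. SAP 8.9 already makes the DR forest plots exploratory, which leaves two tables. The endpoint-specific table in SAP 6.2 lists no Cox analysis for DR. All of this stands and limits the weight of the point. It does not justify the two tables, which still print an unlabelled HR and p-value.

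The second reply is that the reversal depends on assumed inputs. This also stands: the documents give no figure linking drug sensitivity to duration.

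A reader might infer from phase II (30% response on PM01183 versus none on topotecan in platinum-resistant disease) that very unequal responder selection is to be expected here. The documents do not support that strength. That control group had 16 platinum-resistant patients, and 21 of the 29 topotecan patients were on a weekly schedule (protocol 1.3.1). The present control arm is PLD or five-day topotecan, and protocol 1.1 puts single agents at 10–15%. At 0% control response there would be no DR comparison at all.

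**Conclusion.** The point holds. The responder-only HR is biased as a treatment effect whenever response rates differ and duration depends on sensitivity. A reader might go further and conclude that the DR result will run opposite to the truth; that does not follow. Under 12% versus 24% response and 10% true lengthening the median ratio falls to 0.98–0.81, but with a smaller response gap or a larger true lengthening the direction is kept. These sizes rest wholly on assumed models. Nor do the documents support reading this as a threat to the trial's conclusion: the PFS, OS and response comparisons are unaffected. It is a reporting fault in one secondary endpoint, worth correcting because correction is cheap and removes an internal disagreement in the SAP.

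**What to change.** - In SAP 6.2, keep DR in the Kaplan-Meier sentence, but limit the between-arm log-rank and Cox sentences to PFS and OS. Delete the log-rank entry for DR from the summary table. Text, table and shells then agree.
- In Tables 11.3.1.34 and 11.3.1.40, remove the HR and p-values. Report numbers of responders, events and censored patients, with Kaplan-Meier median DR and 95% CI per arm, labelled descriptive.
- Show Figures 11.3.1.50, .51, .58, .59, .66 and .67 without an HR or p-value, or drop them.
- Record the change as a departure from protocol 8.2.1, or align the protocol wording there and in the synopsis.
- If an arm comparison is wanted, compare mean time in response over a pre-specified horizon in all randomised patients, counting zero for non-responders. This is a new analysis, and its horizon must be fixed in advance.

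The cost is SAP wording, a documented departure from the protocol, and no formal DR test. No new data are needed.

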4.1 INCLUSION CRITERIA

- 1) Voluntary written informed consent (IC) of the patient obtained before any study-specific procedure.
- 2) Age \geq 18 years.
- 3) Histologically or cytologically confirmed diagnosis of unresectable epithelial ovarian, fallopian tube or primary peritoneal cancer

- 4) Platinum-resistant disease (PFI: 1-6 months after last platinum-containing chemotherapy).
- 5) Radiologically measurable and/or non-measurable progressive disease according to RECIST v 1.1.
- 6) No more than three prior systemic chemotherapy regimens. Note: in case that a patient had started a new systemic chemotherapy without disease progression to the prior chemotherapy line (e.g., treatment discontinuations due to toxicity; neoadjuvant followed by adjuvant chemotherapy regimens), these two chemotherapy regimens will be considered as one.
- 7) ECOG PS \leq 2 (see [APPENDIX 1](#)).
- 8) Adequate hematological, renal, metabolic and hepatic function:
 - a) Hemoglobin \geq 9 g/dl [patients may have received prior red blood cell (RBC) transfusion]; absolute neutrophil count (ANC) \geq 2.0 \times 10⁹/l, and platelet count \geq 100 \times 10⁹/l.
 - b) Alanine aminotransferase (ALT) and aspartate aminotransferase (AST) \leq 3.0 \times upper limit of normal (ULN).
 - c) Alkaline phosphatase (AP) $<$ 5.0 \times ULN.
 - d) Total bilirubin \leq ULN or direct bilirubin \leq ULN if total bilirubin is $>$ ULN.
 - e) Albumin \geq 3.0 g/dl.
 - f) Calculated creatinine clearance (CrCL) \geq 30 ml/min (using Cockcroft and Gault's formula).
 - g) Creatine phosphokinase (CPK) \leq 2.5 \times ULN.
- 9) At least three weeks since last prior therapy, and grade \leq 1 from any AE derived from previous treatment (excluding grade \leq 2 alopecia or peripheral neuropathy) according to the NCI-CTCAE v. 4.
- 10) Women of childbearing potential must have pregnancy excluded by appropriate testing before study entry. A medically acceptable method of contraception* must be maintained throughout the treatment period and for at least six months after treatment discontinuation.

* Acceptable methods of contraception include intrauterine device (IUD), complete abstinence (non-periodic), oral contraceptive, subdermal implant, or double barrier.

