8.8 Decimal Places, Missing Values and Allowed Assessment Windows

By default, all results will be rounded to one decimal place, except when variables are integer, which will be reported without decimals (e.g., age in years, number of sites, etc.). For representing p-values four decimals will be selected as default but they could be rounded to fewer decimals if necessary.

Missing values will not be included in the calculation of outputs. Assessment windows as specified in the clinical protocol will be respected.

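### The 90% completeness filter for the stepwise models works one covariate at a time and sets no limit on joint patient loss, and two candidates are undefined for some eligible ITT patients

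*SAP*

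**What the plan says.** SAP 6.2 states that the multivariate models "will include all stratification factors and/or prognostic factors/covariates widely reported and recognized by the scientific community", and then names 39 terms including treatment. Those admitted are "All variables with a good percentage of valid cases", with a threshold of approximately 90%. Stepwise selection follows, with 0.05 both to enter and to remove.

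On missing data, SAP 8.8 says: "Missing values will not be included in the calculation of outputs". SAP 8.6 imputes incomplete dates only. Neither section gives an imputation rule or a missing category for covariates.

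The candidates include "measurable disease (yes vs. no), sum of all target lesion diameters" and "time from diagnosis to first infusion". Protocol 4.1 admits "Radiologically measurable and/or non-measurable progressive disease according to RECIST v 1.1", so patients without any target lesion are eligible. SAP 3.1 keeps randomized patients who never received study drug in the ITT population. SAP 11.3 and the summary table in SAP 6.2 place the multivariate models on ITT.

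**The concern.** A filter applied variable by variable says nothing about how many patients are complete on all admitted variables together. A stepwise procedure compares candidates on one common set of patients. In SAS, which SAP 9 names as the software, that set is by default the patients with no gap in any candidate. The fitted models could therefore rest on a selected subset while carrying the ITT label.

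For two candidates the gap is structural rather than accidental. A patient with non-measurable disease only has no target lesions to sum, and a randomized untreated patient has no first infusion. The second variable is also fixed after randomization in an open-label trial, so exclusions through it could differ between arms.

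What is at stake is the reading of Tables 11.3.1.5, 11.3.1.12 and 11.3.1.26 (PFS by IRC, PFS by investigator, OS) and Tables 11.3.1.31 and 11.3.1.37 (response). If an adjusted treatment effect differs from the primary result, the reader cannot tell adjustment from a change in who was analysed. The shells for the Cox tables have no place for patients or events used, so the loss would not show.

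**Working it through.** **The plan's own figures.** The SAP gives no expected analysed number for these models. The related design figure is 332 PFS events (SAP 5.2), from HR 0.70, one-sided 2.5% and 90% power. The Schoenfeld formula gives 4 × (1.960 + 1.282)² / (ln 0.70)² = 331 after rounding up, and 332 events give 90.1% power. That figure is sound and is not in question.

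**Number of candidates.** Counting the list in SAP 6.2 gives 39 terms, which is treatment plus 38 covariates.

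**Joint completeness.** Let N = 420 (SAP 5.2), v the share of valid values per variable, and k the number of incomplete variables. The documents give neither v nor k, so both are assumptions.

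- Nested gaps (the same patients are missing throughout): N × v. With v at least 0.90 this is at least 378, whatever k is.
- Independent gaps: N × v^k.

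| v | k = 3 | k = 5 | k = 10 | k = 38 |
|---|---|---|---|---|
| 99.5% | 414 | 410 | 399 | 347 |
| 99% | 408 | 399 | 380 | 287 |
| 98% | 395 | 380 | 343 | 195 |
| 95% | 360 | 325 | 251 | 60 |
| 90% | 306 | 248 | 146 | 8 |

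For example, 420 × 0.98^10 = 420 × 0.817 = 343. Three variables that each just pass the filter already leave 420 × 0.729 = 306. The k = 38 column is a bound, not an expectation.

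**Target-lesion sum.** Let q be the share of ITT patients with non-measurable disease only. It is not given. If the sum is left missing for them, its valid share is 1 − q.

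- q = 5%: 95% valid, passes the filter, and all 21 patients drop.
- q = 10%: 90% valid, just passes, and all 42 drop.
- q = 15%: 85% valid, fails. The variable leaves the model and none of the 63 drop through it.

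In the first two cases everyone remaining has measurable disease, so the measurable-disease indicator is constant in the model that lists it. In the third, tumour burden is lost as a covariate for all patients. Because the threshold is only approximate, a q near 10% leaves the choice to be made after the data are seen.

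The dropped patients are not a neutral subset. In the protocol's RECIST appendix, the time-point response table for non-target disease only has no partial-response category, so in the response models these are patients who can respond only by complete response.

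**Time to first infusion.** SAP 3.1 includes untreated patients in ITT, and Listing 10.1.5 is planned for them. The variable has no value for them. Table 11.1.1.1 measures the interval from first diagnosis to randomization instead, so the SAP uses two definitions.

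**The case against.** The strongest reply is that the loss may be small and the affected models are secondary.

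- Many candidates should be nearly complete. Performance status, platinum-free interval, prior regimens and albumin are eligibility items, and the first three are also stratification factors. Height, weight, BMI and BSA share the same gaps. Several factors are coded against a residual group, such as "BRCA status (mutated vs. other"), which can absorb unknowns. Partial dates before randomization are imputed.
- SAP 8.8 is a general sentence in a section on decimals and windows. It does not state a complete-case rule for the stepwise models.
- Randomization is to be close to the first dose, so the two diagnosis intervals should differ little in treated patients.
- The primary analysis is the stratified log-rank test, and separate models with only stratification factors and treatment are planned.

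All of this stands, and it limits the size of the point. A reader might infer that the stepwise models will lose a large share of the ITT population, including every patient with non-measurable disease only. The documents do not support that. They give no missingness rates. Heavy losses need many variables with independent gaps. The non-measurable group drops through the sum only if it is about 10% of ITT or less and the sum is left missing.

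The reply does not remove the gap in the plan. No text limits joint loss, and none gives the sum a value when there are no target lesions. Some gaps are plausible: Protocol 5.4 collects prior best response and time to progression only where available, which bears on prior-line PFS and response to last platinum.

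**Conclusion.** The point holds in this limited form. The filter is marginal, covariate missingness is not addressed, and two candidates are undefined for some eligible ITT patients. Followed as written, with usual SAS behaviour, the plan fits models described as ITT on a subset whose size it does not control.

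The size of the loss is not determined by the documents. It is at most about 10% with nested gaps. It is 40 patients (420 − 380) or 77 (420 − 343) with ten independently incomplete variables at 99% or 98% valid, and larger if more variables have gaps. Non-measurable-only patients are either all excluded (up to about 42) or kept at the price of dropping the tumour-burden covariate, depending on which side of about 10% their share falls. The number of untreated patients is unknown.

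This rests on three assumptions: the usual SAS handling of missing covariates, the sum being left missing rather than entered as 0, and the illustrative v, k and q. The primary test and the models with stratification factors and treatment only (Tables 11.3.1.4, 11.3.1.11, 11.3.1.25, 11.3.1.30 and 11.3.1.36) are not affected.

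**What to change.** In SAP 6.2:

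1. Set the target-lesion sum to 0 for patients without target lesions, and enter it alongside the measurable-disease indicator. This keeps both the patients and the covariate, whatever their share.
2. Replace the interval from diagnosis to first infusion with the interval from diagnosis to randomization, as in Table 11.1.1.1.
3. After selection, refit the chosen model on all ITT patients with data on the retained variables, and print patients and events used for both the selection step and the refit.

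Multiple imputation of the remaining covariates is optional. Combining it with stepwise selection has no single agreed pooling rule, so it is not needed to settle this point.

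The cost is SAP wording, a small change to the table shells and modest programming. No new data are needed.
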